8.3.5 Pregnancy

Only pregnancies the Investigator considers to be related to the study intervention (e.g., resulting from a drug interaction with a contraceptive method) are AEs. However, all pregnancies with an estimated conception date during the period defined in Section 8.3.1 (Time Period and Frequency for Collecting Adverse Event and Serious Adverse Event Information) must be recorded in the AE page/section of the eCRF for both pregnancies in female participants and pregnancies in female partners of male participants. The Investigator must notify the Sponsor/designee in an expedited manner of any pregnancy using the Pregnancy Report Form, which must be transmitted by the same process specified for SAE reporting in [Appendix 5 \(Adverse Events: Definitions and Procedures for Recording, Evaluating, Follow-up, and Reporting\)](#), section on Reporting Serious Adverse Events.

Investigators must actively follow up, document and report on the outcome of all these pregnancies, even if the participants are withdrawn from the study.

The Investigator must notify the Sponsor/designee of these outcomes using the Pregnancy Report Form. If an abnormal outcome occurs, the SAE Report Form will be used if the participant sustains an event and the Parent-Child/Fetus Adverse Event Report Form if the child/fetus sustains an event. Any abnormal outcome (e.g., spontaneous abortion, fetal death, stillbirth, congenital anomalies, ectopic pregnancy) must be reported in an expedited manner, as specified in Section 8.3.1 (Time Period and Frequency for Collecting Adverse Event and Serious Event Information), while normal outcomes must be reported within 45 days after delivery.

In the event of a pregnancy in a participant occurring during the study, the participant must be discontinued from the study intervention. The Sponsor/designee must be notified without delay and the participant must be followed as indicated above.

8.4 Treatment of Overdose

For this study, any dose of study intervention greater than the highest daily dose included in the clinical study protocol within a 24-hour time period will be considered an overdose.

Hypoglycemia has not been seen with metformin doses of up to 85 g, although lactic acidosis has occurred in such circumstances. High overdose or concomitant risks of metformin may lead to lactic acidosis. Lactic acidosis is a medical emergency and must be treated in hospital. The most effective method to remove lactate and metformin is hemodialysis and may be used for an overdose.

Even if it not associated with an AE or a SAE, any overdose is recorded in the eCRF and reported to drug safety in an expedited manner. Overdoses are reported on a SAE Report Form, following the procedure in [Appendix 5 \(Adverse Events: Definitions and Procedures for Recording, Evaluating, Follow-up, and Reporting\)](#), section on Reporting Serious Adverse Events.

In this study, metformin will be administered under medical supervision as 2 oral single doses of 500 mg separated by a 7-day wash-out. Overdosage is accordingly unlikely, however in case of overdose, close monitoring will be performed, and adequate medical care will be provided based on the clinical judgment of the Investigator.

8.5 Pharmacokinetics

- The following PK parameters will be calculated, when appropriate:

Parameters will be calculated from the metformin blood concentrations.

Symbol	Definition	Measuring method

AUC _{last}	Area under the plasma concentration versus time data pairs, where _{last} is the time of the last quantifiable concentration	Linear trapezoidal method
AUC _{inf}	Area under the plasma concentration versus time data pairs, with extrapolation to infinity	AUC _{last} + C _{last} / K _{el}
C _{max}	Maximum plasma concentration	Directly observed from the analysis data
T _{max}	Time to maximum plasma concentration	First observed time at which the maximum concentration is observed, directly observed from
t _{1/2}	Elimination half-life	The apparent terminal half-life, calculated according to the equation $t_{1/2} = \ln(2) / K_{el}$ Where K _{el} is the elimination rate constant K _{el} from the linear regression analysis on the log-linear plot of the portion corresponding to the terminal phase of the blood concentration-time curve
AUC _{last} / AUC _{inf}	The ratio of AUC _{last} to AUC _{inf}	AUC _{last} /AUC _{inf}

- The actual date and time (24-hour clock time) of each sample will be recorded to calculate actual time elapsed since the prior dose administration.

Blood sample amount and aliquots per time points of pharmacokinetics are as follows.

Part 1: Fasted state

Collection time (h)	0	0.5	1	2	2.5	3	3.5	4	5	6	7	8	10	12	24	32
Sample amount (mL)	5	5	5	5	5	5	5	5	5	5	5	5	5	5	5	5
Aliquots	2	2	2	2	2	2	2	2	2	2	2	2	2	2	2	2

Part 2: Fed state

Collection time (h)	0	1	2	3	4	5	5.5	6	6.5	7	8	9	10	12	24	32
Sample amount (mL)	5	5	5	5	5	5	5	5	5	5	5	5	5	5	5	5
Aliquots	2	2	2	2	2	2	2	2	2	2	2	2	2	2	2	2

- The quantification of metformin in plasma will be performed using a validated analytical method (UPLC-MS/MS; LLOQ 20 ng/mL). Concentrations will be used to evaluate the PK of metformin.
- Remaining samples collected for analyses of metformin concentration may also be used to evaluate safety or efficacy aspects related to concerns arising during or after the study.
- Details on processes for collection and shipment of these samples are in the SOP of Clinical Facility. Retention time and possible analyses of samples after the end of study are specified in the respective ICF.

1) Blood Collection Method

A normal saline-locked catheter will be inserted into the vein of arm or hand of the participants before dosing on Day 1 of each Period. 1 mL of the collected blood will be discarded to remove the saline left in the collection set and after that, collect blood into the EDTA(K2) treated collection tube. About 1 mL of physiological saline is injected into the catheter to prevent blood coagulation.

2) Place and Person for Blood Collection

The collection site should be a place where about 60 people can be active, taking into consideration the space required for blood collection management and blood collection of 48 participants for Part 1 and 34 participants for Part 2. It is conducted within the Clinical Trial Center (PPD) of Chungnam National University Hospital, which is separated from general patients.

Blood collection and management personnel include a Principal Investigator (or delegated investigator), a Clinical Trial Pharmacist, nurse(s), an assistant for the blood collection and a participant management personnel who is responsible for checking the randomization number of each participant and to arrange the order of blood samples collection. A total of more than 7 people are expected to be involved.

3) Measures to Prevent Infections When Collect Blood Sample

The collection of blood samples from participants will be done in a room with limited access to the public. Single use sterilized apparatus will be used to collect blood samples. The disposable blood collection apparatus will be disposed in a biohazard box. Needle-

stick injury will be managed according to the Infection Management Procedure of Chungnam National University Hospital.

4) Allowable Pharmacokinetics Blood Collection Time

Every effort should be made to ensure that the pharmacokinetics blood sample is collected at nominal time following administration of the study interventions. The exact time of sample collection must be recorded in the source document and eCRF. The actual time of blood collection may be different from the nominal time, but the number of samples should remain the same.

In the case of deviation of the blood sampling from the planned time point specified in this protocol, details such as the actual blood sampling time should be recorded in the eCRF. The acceptance range according to each sampling time point is as follows.

Part 1: Fasted state

Day (per period)	Time (h)	Deviation
1	0	-1 h
	0.5	
	1	
	2	
	2.5	
	3	
	3.5	
	4	
	5	
	6	
	7	
	8	
	10	
	12	
2	24	±10 min
	32	±30 min

Part 2: Fed state

Day (per period)	Time (h)	Deviation
1	0	-1 h

	1	
	2	
	3	
	4	
	5	
	5.5	
	6	±5 min
	6.5	
	7	
	8	
	9	
	10	
	12	
2	24	±10 min
	32	±30 min

Refer to '9. Statistical Considerations' for details when performing statistical processing on primary variables.

5) Plasma Storage for Pharmacokinetic Analysis

Blood for pharmacokinetic analysis will be stored in an ice bath immediately after collection and centrifuged (CCI [REDACTED]) within 30 minutes from the collection time to isolate the upper plasma. About 0.6 mL of the separated plasma will be transferred into 2 polypropylene tubes (one for analysis, one as back-up) and stored in a freezer set at CCI [REDACTED] until they are ready to be transferred to the Analytical Facility.

6) Transportation of Pharmacokinetic Samples

Samples stored at CCI [REDACTED] or below are transferred from the Clinical Facility to the Analytical Facility. At the Analytical Facility, continue to store the samples at CCI [REDACTED] until the date of product approval by MFDS. Details of blood sample preparation, aliquot dispensing, sample storage and transportation shall be in accordance with Sample Treatment and Transfer Manual. The sample shall not be used for any purpose other than for this bioequivalence study and shall be discarded in consultation with the Sponsor after product approval.

7) Analysis of Concentration of Metformin in Plasma

Analysis of metformin in plasma is done by using ultraperformance liquid chromatography-tandem mass spectrometry (UPLC-MS/MS) (LLOQ: 20 ng/mL). After

validation of the analytical method is completed, the analytical method will be applied to the sample analysis.

[figure not shown]
Method validation is performed in accordance with the “Guideline on Bioanalytical Method Validation” (MFDS, December 2013).

Reanalysis should be completed before the pharmacokinetic analysis or statistical analysis. Sample reanalysis is performed only when the sample analysis result falls in the criteria specified in the PPD SOP titled “Reanalysis, Reinjection Analysis and Reintegration”.

After the sample analysis is completed, Incurred Sample Reanalysis (ISR) is performed in accordance with ‘5. Incurred Sample Reanalysis’ of the “Guideline on Bioanalytical Method Validation” (MFDS, December 2013) and Standard Operating Procedure of PPD

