4.1.2 Rationale for determination of Pharmacokinetics Time Points

Idkaidek et al (1) provided the following pharmacokinetic parameters of oral metformin 750 mg XR in healthy adults:

Formulation / Pharmacokinetic parameter	XR-Fasted	XR-Fed
C_{max} (ng/mL)	832 (300)	794 (143)
T_{max} (h)	4.3 (1.0)	6.35 (1.1)
$t_{1/2}$ (h)	3.8 (1.2)	3.66 (0.8)

Metformin mean (SD) plasma pharmacokinetic parameters after 750 mg XR (Extended Release) oral doses to healthy volunteers

In the Article 15 (2) of the Korean guideline "Standard on Pharmaceutical Equivalence Study"¹², it is mentioned that "Blood collection shall be conducted with sufficient time period of more than 3 times the elimination half-life or AUC_{0-t} to reach at least 80% of AUC_{∞} .". It is recommended that blood sampling needs more than 12 times and more than twice blood collection before reaching to the highest blood concentration (C_{max})."

To reflect this requirements, the blood collection time period shall be 32 hours which is more than 3 times the elimination half-life, and totally 16 blood samples will be collected as in below.

1) Part 1 (Fasted state)

- Number of samples: 16 times (once just before administration of study intervention, 15 times thereafter)
- Sampling time: Before administration (just prior to administration) of study

intervention and 0.5, 1, 2, 2.5, 3, 3.5, 4, 5, 6, 7, 8, 10, 12, 24 and 32 hours thereafter
2) Part 2 (Fed state)

- Number of samples: 16 times (once just before administration of study intervention, 15 times thereafter)
- Sampling time: Before administration (just prior to administration) of study intervention and 1, 2, 3, 4, 5, 5.5, 6, 6.5, 7, 8, 9, 10, 12, 24 and 32 hours thereafter

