9.4.3 Other Analyses

9.4.3.1 Analysis of Primary Endpoints

Primary Variables: AUC_{last} and C_{max} of metformin

- An analysis of variance (ANOVA) model will be fitted for the log-transformed PK parameters C_{max} and AUC_{last} based on the PK analysis set. The model will include treatment, period, sequence, and participant within sequence as fixed effects. Treatment differences on the log scale will be estimated for C_{max} and AUC_{last} together with their 90% CIs. Point estimates and CIs will be back-transformed to the original scale for the comparisons.

The comparison will be the test treatment (Glucophage® XR Reduced Mass tablet) vs the reference treatment (Glucophage® XR tablet) under fasting conditions in Part 1, and under fed conditions in Part 2. The null hypothesis for non-bioequivalence will be rejected if the 90% CI for the ratio of the GeoMean lies within the interval 0.8000 to 1.2500 for all primary pharmacokinetic parameters.

The primary endpoints will be descriptively analyzed and graphical displays will be prepared. PK analyses will be specified in the Integrated Analysis Plan finalized before database lock.

In principle, analysis of variance shall be used at α (significance level) = 0.05.

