9.4.3.2 Analysis of Secondary Endpoints

Secondary Variables: AUC_{inf} (if data allows to calculate), AUC_{last}/AUC_{inf} (if data allows to calculate), $t_{1/2}$ (if data allows to calculate) and T_{max} of metformin. AUC_{inf} will be analyzed in the same way as the primary PK parameters.

The secondary endpoints will be descriptively analyzed and graphical displays will be also prepared where appropriate.

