Appendix 7 Pharmacokinetic Parameters

Symbol	Definition
AUC _{last}	The area under the concentration-time curve (AUC) from time zero (= dosing time) to the last sampling time (t_{last}) at which the concentration is at or above the lower limit of quantification. Calculated using the linear trapezoidal rule
AUC _{inf}	The AUC from time zero (dosing time) extrapolated to infinity, based on the predicted value for the concentration at t_{last} , as estimated using the linear regression from λ_z determination. $AUC_{inf} = AUC_{last} + C_{last\ pred}/\lambda_z$
C _{max}	Maximum observed concentration
λ_z	Terminal first order (elimination) rate constant. Determined from the terminal slope of the log-transformed concentration curve using linear regression on terminal data points of the curve
$t_{1/2}$	Apparent terminal half-life. $t_{1/2} = \ln(2)/\lambda_z$
t_{max}	The time to reach the maximum observed concentration collected during a dosing interval (unless otherwise defined, take the 1 st occurrence in case of multiple/identical C _{max} values)
AUC _{last} /AUC _{inf}	The ratio of AUC _{last} to AUC _{inf}

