5. PHARMACOKINETIC AND SAFETY VARIABLES

5.1 PHARMACOKINETIC ENDPOINTS

Blood collection for pharmacokinetic analysis follows the schedule given in the BE Study Protocol. Pharmacokinetic parameters are calculated from the blood concentration-time data of 'metformin' using a non-compartmental method.

Parameter	Definition	Measuring method
AUC_{last}	Area under the plasma concentration versus time data pairs, where last is the time of the last quantifiable concentration	Linear trapezoidal method
AUC_{inf}	Area under the plasma concentration versus time data pairs, with extrapolation to infinity	$AUC_{last} + C_{last} / K_{el}$
C_{max}	Maximum plasma concentration	Directly observed from the analysis data.
T_{max}	Time to maximum plasma concentration	First observed time at which the maximum concentration is observed. Directly observed from the analysis data.
$t_{1/2}$	Elimination half-life	The apparent terminal half-life, calculated according to the equation $t_{1/2} = \ln(2) / K_{el}$ Where K_{el} is the elimination rate constant K_{el} from the linear regression analysis on the log-linear plot of the portion corresponding to the terminal phase of the blood concentration-time curve.
AUC_{last} / AUC_{inf}	The ratio of AUC_{last} to AUC_{inf}	AUC_{last} / AUC_{inf}

Type	PK Parameters
Primary endpoints	AUC _{last} , C _{max}
Secondary endpoints	AUC _{inf} (if data allows to calculate), AUC _{last} /AUC _{inf} (if data allows to calculate), t _{1/2} (if data allows to calculate) and T _{max}

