7.2.3 Pharmacokinetic Analysis

The population for pharmacokinetic analysis is pharmacokinetics assessment group.

AUC_{last} and C_{max} , AUC_{inf} (if data allows to calculate), $t_{1/2}$, converted to natural logs are analyzed using an analysis of variance (ANOVA) model having sequence group, subject (sequence group), period, and dosing group effects. In principle, analysis of variance shall be used at α (significance level) = 0.05. The mean square error (MSE) is then used for the %CV calculation.

Using the ANOVA results, the point estimate of the mean difference (T-R) and the corresponding 90% confidence interval are calculated, and they are indexed to calculate the point estimate of the geometric mean ratio (T/R) and the 90% confidence interval.

T_{max} presents the median of the reference drug and the test drug, and p-value is calculated through the Wilcoxon signed-rank test.

Pharmacokinetics parameters are summarized and listed according to the dosing group.

PK parameter	Summary statistics
AUC_{last} , C_{max} , AUC_{inf} , T_{max} , $t_{1/2}$, AUC_{last}/AUC_{inf}	N, Arithmetic Mean, Standard Deviation, Median, Minimum, Maximum, Geometric Mean, Geometric Coefficient of Variation

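### Do the two AUCinf formulas, the unplanned half-life ANOVA and the unstated terminal-slope rule call for a change to the plan?

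*Protocol*

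**What the plan says.** **AUCinf.** Protocol 8.5 and SAP 5.1 share one definition, "Area under the plasma concentration versus time data pairs, with extrapolation to infinity", and one formula, AUClast + Clast/Kel. Protocol Appendix 7 describes AUCinf as "extrapolated to infinity, based on the predicted value for the concentration at" the last quantifiable time, with formula AUClast + predicted Clast/λz. Kel and λz are the same rate constant under two names.

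**Terminal slope.** Kel comes "from the linear regression analysis on the log-linear plot of the portion corresponding to the terminal phase of the blood concentration-time curve" (SAP 5.1; Protocol 8.5 agrees). No minimum number of points, fit criterion or extrapolation limit is given. AUCinf, AUClast/AUCinf and half-life are to be reported only where the data permit. SAP 6.3 reports a parameter that cannot be calculated as NC and treats it as missing.

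**Analysis.** Protocol 9.4.3.2 says that AUCinf "will be analyzed in the same way as the primary PK parameters" and then that "The secondary endpoints will be descriptively analyzed". SAP 7.2.3 lists half-life with AUClast, Cmax and AUCinf as parameters that, "converted to natural logs are analyzed using an analysis of variance (ANOVA) model having sequence group" and the other crossover effects.

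**Where detail may sit.** Protocol 9.4.3.1 states that "PK analyses will be specified in the Integrated Analysis Plan finalized before database lock". SAP 2 says the analysis follows the CRO's SOP as well as the Protocol, and SAP 7.1 and 7.2 place detail for each parameter in appendix mock-ups. None of these is in the supplied text.

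**The concern.** Two sections of the current Protocol give AUCinf formulas that need not agree. The SAP's only precedence rule covers SAP against SOP, so it does not settle the matter. The SAP also adds an inferential output for half-life that the Protocol treats descriptively, and its ANOVA sentence leaves out the data-permitting condition that SAP 5.1 attaches to half-life.

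The slope rule looked the most serious. There is no sample between 12 h and 24 h, and the assay limit is 20 ng/mL. Many profiles might end at 12 h with a sizeable extrapolated area, so an unstated acceptance rule could decide who enters the AUCinf comparison. Protocol 6.3.2 has statistical analysis start after the sample codes are released, so a rule chosen late could in principle be chosen with the results in view. At stake would be the reproducibility of the AUCinf and half-life comparisons.

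**Working it through.** The plan states no figure on this point to reproduce. The check sizes each part.

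**Inputs.** Protocol 4.1.2 gives means after 750 mg XR: fasted Cmax 832 ng/mL, Tmax 4.3 h, half-life 3.8 h; fed 794 ng/mL, 6.35 h, 3.66 h. Sampling times and the 20 ng/mL limit are in Protocol 8.5. Evaluable numbers (38, 22) and within-participant AUClast CVs (19.1%, 13.1%) are in Protocol 9.2.2. Assumptions: linear rise to Tmax, then mono-exponential decline, with Cmax scaled by 500/750 except where marked unscaled.

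**Step 1: where the mean profile ends.** k = ln 2/half-life = 0.1824 per h fasted and 0.1894 fed. C(24) = Cmax × exp[−k(24 − Tmax)].

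| | Fasted | Fed |
|---|---|---|
| C(24), scaled to 500 mg | 15.3 | 18.7 |
| C(24), unscaled | 22.9 | 28.1 |
| AUClast/AUCinf, last point 12 h | 3,476/(3,476 + 746) = 82.3% | 3,521/(3,521 + 959) = 78.6% |
| AUClast/AUCinf, last point 24 h | about 98% | about 98% |

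Concentrations are in ng/mL and areas use the linear trapezoid on the planned times. Scaled, the mean profile ends at 12 h; unscaled, it ends at 24 h. The ratio itself does not depend on dose once the last point is fixed. The apparent straddling of 80% therefore depends on the scaling assumption.

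**Step 2: observed or predicted Clast.** If observed Clast differs from predicted by 10%, one participant's AUCinf changes by 10% of the extrapolated share: 10% × 17.7% = 1.8% fasted and 10% × 21.4% = 2.1% fed at 12 h. At 24 h the change is about 0.2%. For the ratio, suppose every profile ends at 12 h and the 10% is an independent SD in each period. The 95% shift is then 1.96 × √2 × 1.77%/√38 = 0.8% fasted and 1.96 × √2 × 2.14%/√22 = 1.3% fed. A simulation tuned to the Protocol 9.2.2 CVs, in which profiles end at different times, gave 0.15% to 0.88%.

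**Step 3: the half-life ANOVA.** Protocol 9.1 limits the comparative parameters to AUClast and Cmax. SAP 3.1 counts eight null hypotheses: two one-sided tests × two parameters (AUC and Cmax) × two parts. Half-life is in neither. The missing condition changes nothing, because SAP 5.1 already attaches it and SAP 6.3 removes values that cannot be calculated.

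**Step 4: the 80% figure.** The guideline text quoted in Protocol 4.1.2 asks that sampling last for more than three half-lives, or long enough for AUC to time t "to reach at least 80% of" the AUC to infinity. It concerns sampling duration. The Protocol meets it through the half-life alternative: 3 × 3.8 = 11.4 h against 32 h. Neither document uses 80% to accept or reject a participant's AUCinf.

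**Step 5: what an 80% filter would do anyway.** In the dose-scaled simulation, a three-point minimum plus an 80% filter removed 5 to 9 of 38 fasted participants and 1.4 to 7 of 22 fed. Adding the filter moved the AUCinf ratio by about 3% to 5% and 2% to 7% (95% range). Compare dropping m participants at random, using AUClast variability: shift = 1.96 × √[2s²(1/(n − m) − 1/n)], with s² = ln(1 + CV²) = 0.0358 fasted and 0.0170 fed.

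- Fasted, n = 38: m = 5 gives 3.3%; m = 9 gives 4.7%.
- Fed, n = 22: m = 1.4 gives 2.0%; m = 7 gives 5.3%.

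Smaller n alone accounts for the fasted movement and most of the fed. For scale, the 90% CI half-width for AUClast is t × √(2s²/n): 1.688 × 0.0434 = 0.073 fasted and 1.725 × 0.0393 = 0.068 fed on the log scale, about 7% to 8% as a ratio.

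**The case for a change.** The best case for a change is that every textual difference is on the page, the remedy is a sentence or a citation, and fixing slope rules before the codes are released removes any room for choice. The slope method does matter more than the formula. In the simulation, taking the last three points instead of the best adjusted R² moved the half-life test/reference ratio by 2% to 8% fasted and 2% to 14% fed.

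The textual differences stand, and so does the point that these two comparisons cannot be rebuilt from the two documents alone. That last point is weak evidence of a gap, because the SOP, the Integrated Analysis Plan and the SAP mock-ups are not in the supplied text, and terminal-slope conventions would ordinarily be found there. No specific slope rule is shown to be better than the one the analysts will use. The room for choice touches only outputs on which no conclusion rests.

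On the formula, Appendix 7 can be read as specifying what 8.5 leaves generic, since 8.5 never says that Clast is observed. On half-life, Protocol 9.4 leaves analysis detail to the SAP, and a supportive estimate does not displace the descriptive summary, which SAP 7.2.3 also provides.

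**Conclusion.** No change to the plan follows. The formula difference is a drafting slip, with an effect on the AUCinf ratio of about 0.2% to 0.9% in simulation and at most about 1.3% in the hand calculation. The half-life ANOVA is an unlabelled supportive addition that feeds no decision. The slope and acceptance rule is ordinary non-compartmental detail that analysts can settle from their SOP or the Integrated Analysis Plan, and the larger shifts attached to an 80% filter describe a rule the documents do not contain.

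The bioequivalence conclusion is untouched: AUClast is the trapezoidal area to the last quantifiable sample and Cmax is read directly from the data. That holds whatever the simulation assumes. The sizes for AUCinf and half-life do depend on assumptions: scaling from 750 mg to 500 mg, the shape of absorption, 10% to 15% residual error, an 8% within-participant CV for the rate constant, and the attribution of extra Cmax variability to input duration.
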